^b Adverse event monitoring should include the collection of all adverse events through follow-up in all patients, including those who have discontinued study treatment but are continuing in the study. Positive pregnancy and partner pregnancy information up to 90 days after last study drug administration will be collected.

^c Viral loads of AdV, BKV, CMV, HHV-6, and JCV in plasma and in PCMBs for EBV will be measured and evaluated at the central lab. Additional post-infusion samples may be collected if clinically indicated. If patient develops any clinically significant infection of AdV, BKV, CMV, EBV, HHV-6, or JCV at any point during the study periods, infection assessments should be completed prior to initiating standard of care therapy (see [Section 8.3](#)).

^d Patient peripheral blood mononuclear cells will be assessed for the presence of virus-reactive T cells using enzyme-linked immunospot.

^e The infection assessment will be performed for all patients who require either treatment for disease or initiation of preemptive therapy during both the primary study period and the follow-up period through Week 26 ([Section 8.3](#)). It is very important to ensure that all procedures, as outlined in the SoA, are performed immediately prior to the initiation of treatment of viral diseases or initiation of preemptive therapy (ie, on the day anti-viral therapy is initiated). Most importantly, a plasma sample for AdV, BKV, CMV, HHV-6, and JCV and a PCMB sample for EBV for PCR testing at the central laboratory should be collected. After developing an infection, such patients will continue to be followed in the study and complete all remaining visits through Week 26.

^f Assessment of quality of life (using FACT-BMT, EQ-5D-5L, EQ-5D-Y, and EQ-5D-Y Proxy Version 1questionnaires, as age-appropriate) should be completed prior to any study procedures at this visit.

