Patients will be tested once a week by the central laboratory during Screening until treatment assignment, using polymerase chain reaction (PCR) assays for each virus. Cohort OL will include patients with and without detectable AdV, BKV, CMV, EBV, HHV-6, and JCV viremia. After Cohort OL, Cohort A will include patients without detectable AdV, BKV, CMV, EBV, HHV-6, and JCV viremia (ie, below the level of quantitation) based on the last viral load assessment available within 7 days prior to randomization, and Cohort B will include patients who are positive with AdV, BKV, CMV, EBV, HHV-6, and/or JCV viremia based on the last viral load available within 7 days prior to randomization, as documented by central laboratory test results. Randomization will occur prior to Day 1. Patients who are positive for >3 viruses will not be eligible to participate.

After HCT, eligible patients in Cohort A and Cohort B will receive either ALVR105 (████████ for patients <40 kg or ██████████ for patients ≥ 40 kg, every 14 days) or placebo every 14 days. Patients in Cohort OL will receive ALVR105 (████████ for patients <40 kg or ██████████ for patients ≥ 40 kg, every 14 days for 14 weeks. Treatment with either ALVR105 or placebo will begin between 15 to 42 (+7) days post-HCT and will continue for 14 weeks. The total duration of patient participation is approximately 28 to 32 weeks, including up to 6 weeks for screening, the 14-week treatment period, and 12 weeks of follow-up.

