1.3. Schedules of Activities

Table 1: Schedule of Activities—Pre-screening Period and Screening Period (All Cohorts)

	Pre-screening Visit ^a	Pre-screening Period ^a	Screening Visit ^b	Screening Period ^b
Study Week	NA	Weekly Visits	Up to 6 weeks before Study Drug Administration	Weekly after Screening Visit until Study Drug Administration
Study Day	NA	NA	May be from Day -42 to Study Drug Administration Day	May be from Day -42 to Study Drug Administration Day
Visit Window (Days)	NA	±3	NA	±3
Study Procedures				
Informed consent/assent ^c	X		X	
I/E criteria	X ^d		X	
Demographics			X	
Medical history ^d			X	
Documentation of HLA typing ^e			X	
Prior and concomitant medications including			X	X

	Pre-screening Visit ^a	Pre-screening Period ^a	Screening Visit ^b	Screening Period ^b
Study Week	NA	Weekly Visits	Up to 6 weeks before Study Drug Administration	Weekly after Screening Visit until Study Drug Administration
Study Day	NA	NA	May be from Day -42 to Study Drug Administration Day	May be from Day -42 to Study Drug Administration Day
Visit Window (Days)	NA	±3	NA	±3
conditioning regimen for HCT				
Adverse events ^f			X	X
Complete physical examination			X	
Weight and height ^g			X	
Vital signs ^h			X	
12-lead ECG			X	
Clinical labs ⁱ			X	
Pregnancy test ^j			X	
Testing for HIV, HCV, HBV ^k			X	

	Pre-screening Visit ^a	Pre-screening Period ^a	Screening Visit ^b	Screening Period ^b
Study Week	NA	Weekly Visits	Up to 6 weeks before Study Drug Administration	Weekly after Screening Visit until Study Drug Administration
Study Day	NA	NA	May be from Day -42 to Study Drug Administration Day	May be from Day -42 to Study Drug Administration Day
Visit Window (Days)	NA	±3	NA	±3
BKV, AdV, CMV, JCV, EBV, and HHV-6 viral load ^l	X	X	X	X ^m

Abbreviations: AdV = adenovirus; ALT = alanine aminotransferase; AST = aspartate aminotransferase; ; β-HCG = beta human chorionic gonadotropin; BKV = BK virus; CBC = complete blood count; CMV = cytomegalovirus; EBV = Epstein-Barr virus; ECG = electrocardiogram; GGT = gamma-glutamyltransferase; HBV = hepatitis B virus; HCV = hepatitis C virus; HIV = human immunodeficiency virus; HHV-6 = human herpesvirus 6; HLA = human leukocyte antigen; I/E = inclusion and exclusion; JCV = JC virus; LFT = liver function test; NA = not applicable; PBMCs = peripheral blood mononuclear cells

Note: Visits may be done via a home health visit as agreed with the Sponsor. Please see the Study Manual for more information.

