^a Adult patients and pediatric patients ≥12 years old may participate in an optional pre-screening period that may begin up to 4 weeks prior to administration of conditioning for HCT and continue until there is a decision on whether to screen for the study. Viremia testing during pre-screening will begin after HCT and will continue weekly, if possible. Pre- screening is not required for eligibility.

^b The Screening Visit could occur any time between the day of HCT and up to 42 (+7) days post-HCT. When this visit occurs during this time period may vary by patient depending upon when the decision is made to participate in the study.

^c Prior to conducting any study-related activities, written informed consent/assent to participate in the study must be provided by the patient and/or patient's guardian. The ICF for the pre-screening period is separate from the ICF that is signed at Screening Visit for study participation.

^d To include CMV sero status of both patient and HCT donor

^e The HLA type of the patient and their HCT cell donor(s) will be obtained from the medical record.

^f Adverse events will be monitored and documented from signing of the ICF for study participation until study participation is complete.

^g Height and weight will be measured at screening. At later assessments during the Treatment Period, only weight will be assessed.

^h Includes body temperature, blood pressure, heart rate, O₂ saturation, and respiration rate and will be measured after resting for 5 minutes.

ⁱ Clinical laboratory assessments collected as part of standard of care may be used to fulfill these requirements. CBC must include differential and LFTs must include alkaline phosphatase, bilirubin (total and direct), GGT, AST, and ALT. Urinalysis must be performed. Laboratory safety evaluations (hematology, chemistry, and urinalysis) specified in [Section 8.4.4](#) will be performed prior to study therapy initiation. These samples will be sent to the appropriate central laboratory(ies) following the procedure(s) described in the study manual(s).

^j For female patients, at Screening a β-HCG blood test will be performed. A urine pregnancy test will also be performed at the site prior to study therapy initiation (SoA for Treatment Period, [Table 2](#)).

^k Serum will be screened for HIV, HBV, and HCV antibodies with reflex nucleic acid testing of plasma. Medical records of previous testing in the last 3-6 months may be used.

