^l Viral loads of BKV, AdV, CMV, JCV, and HHV-6 in plasma and of EBV in PCMBs will be measured weekly for adult patients and pediatric patients ≥ 12 years old after allogenic HCT conditioning during pre-screening period and screening period until treatment assignment, if possible. Pediatric patients < 12 years old will have only one blood draw during the Screening visit and will not have weekly blood draws during the screening period. Viral load testing should NOT be done on day of HCT during pre-screening. The results of the repeat analyses from the screening period must be available at the time of treatment assignment, unless the timing of the Screening Visit is 1 week or less before treatment administration. Results of central laboratory testing for viral load will be used for the purpose of determining eligibility/inclusion.

^m Adult patients and pediatric patients ≥ 12 years old only

Table 2: Schedule of Activities – Treatment -- Period 1 for Patients ≥12 Years of Age (Week 1 to 14, All Cohorts)

Time Period	Treatment Assignment	Study Drug Administration Day	Treatment Period													
			Wk 1	Wk 2	Wk 3	Wk 4	Wk 5	Wk 6	Wk 7	Wk 8	Wk 9	Wk 10	Wk 11	Wk 12	Wk 13	Wk 14
Study Day		1 ^a	8	14	21	28	35	42	49	56	63	70	77	84	91	98
Visit Window (Days)		NA ^b	±3	±5	±3	±5	±3	±5	±3	±5	±3	±5	±3	±5	±3	±3
Study Procedures																
Review of I/E criteria		X														
Prior & concomitant medications as well as conditioning regimen for HCT		X		X		X		X		X		X		X		X
Adverse events ^c		X		X		X		X		X		X		X		X
Physical examination ^d		X		X		X		X		X		X		X		X
Weight		X			X			X			X			X		X
Vital signs ^e		X		X		X		X		X		X		X		X
12-lead ECG ^f		X		X		X		X		X		X		X		X
Clinical labs ^g		X		X		X		X		X		X		X		X
Pregnancy test ^h		X		X		X		X		X		X		X		

Time Period	Treatment Assignment	Study Drug Administration Day	Treatment Period													
			Wk 1	Wk 2	Wk 3	Wk 4	Wk 5	Wk 6	Wk 7	Wk 8	Wk 9	Wk 10	Wk 11	Wk 12	Wk 13	Wk 14
Study Day		1 ^a	8	14	21	28	35	42	49	56	63	70	77	84	91	98
Visit Window (Days)		NA	±3	±5	±3	±5	±3	±5	±3	±5	±3	±5	±3	±5	±3	±3
Study Procedures																
BKV, AdV, CMV, JCV, and HHV-6 viral load ⁱ			X	X	X	X	X	X	X	X	X	X	X	X	X	X
EBV PCMBs ⁱ		X	X	X	X	X	X	X	X	X	X	X	X	X	X	X
Treatment Assignment ^j	X															
Virus-Specific T Cell Assessment ^k		X				X		X			X			X		X
Study treatment administration ^l		X		X		X		X		X		X		X		
Post infusion monitoring ^m		X		X		X		X		X		X		X		
Infection assessment ⁿ		X	X	X	X	X	X	X	X	X	X	X	X	X	X	X

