^gClinical laboratory assessments collected as part of standard of care may be used to fulfill these requirements. CBC must include differential and LFTs must include alkaline phosphatase, bilirubin (direct and indirect); GGT, AST, and ALT. Urinalysis must be performed. Laboratory safety evaluations (hematology, chemistry, and urinalysis) specified in [Section 8.4.4](#) will be performed prior to study drug initiation. These samples will be sent to the appropriate central laboratory(ies) following the procedure(s) described in the study manual(s).

^hFor female patients who are of childbearing potential, a urine pregnancy test will be performed at the site prior to study therapy initiation. If the urine pregnancy test result is negative, the patient will be eligible for treatment assignment and the remainder of the Day 1 testing/procedures will be performed. If the urine pregnancy result is positive, the patient must not be assigned to treatment and should reflex to a β-HCG blood test before screen failing. A urine pregnancy test will be performed prior to each treatment for female patients who are of childbearing potential.

ⁱViral loads of AdV, BKV, CMV, JCV, and HHV-6 in plasma and of EBV in PCMBs will be measured. See the Laboratory Manual for more detailed information on volume of blood draws. Additional post-infusion samples may be collected, as clinically indicated. If patient develops any clinically significant infection of AdV, BKV, CMV, EBV, HHV-6, or JCV at any point during the study periods, infection assessments should be followed prior to initiating standard of care therapy (see [Section 8.3](#)).

^jPatients in Cohort OL will be assigned to ALVR105. Patients in Cohorts A and B will be randomized to either ALVR105 or placebo based upon the last viral load assessed and within 7 days of randomization. Treatment assignment will be about 2 to 3 days before Day 1.

^kPatient peripheral blood mononuclear cells will be assessed for the presence of virus-reactive T cells using enzyme-linked immunospot.

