2.3.2. Potential Risks

ALVR105 primarily targets cells infected with AdV, BKV (and/or JCV), CMV, EBV, and/or HHV-6. The main risks of administration are inflammation at sites of existing disease or GVHD due to cross-reactivity with the recipient's HLA antigens. Adverse events attributable to virus-specific T cell administration may potentially occur in a small percentage of the treated population. These can include both hematologic and non-hematologic effects, as reported in the CHARMs

study.

Studies of donor-derived virus-specific T cells suggest that virus-specific T cells do not persist in patients who receive methylprednisolone in doses ≥ 1 mg/kg/day. Therefore, if patients develop severe inflammatory reactions thought to be attributable to ALVR105, a therapeutic option is to administer methylprednisolone (1 to 2 mg/kg/day). In patients who develop skin rash or skin GVHD, excellent responses have been noted with the administration of topical steroids.

As with other biological therapies delivered by IV infusion, the side effects of ALVR105 infusion include allergic reactions (anaphylaxis), decreased oxygenation, nausea/vomiting, arrhythmia, and hypotension.

A detailed breakdown of the timepoints and blood volumes to be collected during the course of this study is provided in the Laboratory Manual.

In order to minimize the volume of blood collected during the study trial, the blood volume of individual samples has been reduced to the maximum extent feasible wherever possible. This has been performed in a manner that is expected to maintain the scientific integrity of the study and related data, while minimizing the risks to the patients.

In order to minimize the volume of blood collected during the study, especially for pediatric patients, the blood volume of individual samples has been reduced to the maximum extent feasible wherever possible. For pediatric patients < 12 years of age, collection of blood samples for the evaluation of viral load for all six viruses (AdV, BKV, CMV, EBV, and/or HHV-6, and JCV) is limited to every other week and blood volume is sufficient for testing only AdV viremia in the other weeks. Pediatric patients also do not participate in pre-screening blood samples. This reduction in volume of blood collection has been done in a manner that is expected to maintain the scientific integrity of the study while minimizing the risks to patients. For maximum blood draw volumes, see the Laboratory Manual.

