5.2. Exclusion Criteria

Patients who meet any of the following criteria will be excluded from participation in the study:

Medical Conditions

1. Has a history of AdV, BKV, CMV, EBV, HHV-6, and/or JCV end-organ disease within 6 months prior to treatment assignment
2. Has evidence of AdV, BKV, CMV, EBV, HHV-6, and/or JCV viremia for more than 3 viruses, from a central or local laboratory at any time during Screening prior to treatment assignment
3. Evidence of active Grade >2 acute GVHD (for additional information on acute GVHD grading and severity, see Appendix 5 [[Section 10.5](#)] or CRS Appendix 6 [[Section 10.6](#)], respectively).
4. Presence of non-minor uncontrolled or progressive bacterial or fungal infections (ie, evidence of bacteremia, fungemia, disseminated, and/or organ-specific infection not well controlled by present therapies)
5. Presence of progressive, uncontrolled viral infections with evidence of end organ disease
6. Known history or current (suspected) diagnosis requiring treatment of CRS associated with the administration of peptides, proteins, and/or antibodies
7. Evidence of encephalopathy at screening
8. Relapse of primary malignancy other than minimal residual disease.

Prior/Concomitant Therapy

9. Donor lymphocyte infusion performed within 21 days prior to randomization
10. Received within 7 days prior to treatment assignment any of the following: ganciclovir, valganciclovir, foscarnet, acyclovir (at doses >3200 mg PO per day or >25 mg/kg IV per day), valacyclovir (at doses >3000 mg PO per day), famciclovir (at doses >1500 mg PO per day)
11. Received any investigational antiviral agent/biologic therapy within 30 days prior to screening or plans to receive during the study any of the following: cidofovir, CMV hyper-immune globulin, or any investigational CMV antiviral agent/biologic therapy.
12. Ongoing therapy with high-dose systemic corticosteroids (ie, prednisone equivalent dose >0.5 mg/kg/day) within 7 days prior to screening
13. Prior therapy with antithymocyte globulin, alemtuzumab (Campath-1H), or other immunosuppressive T cell-targeted monoclonal antibodies within 28 days of treatment assignment
14. Receipt of mechanical ventilation of any type, within 1 month prior to the administration of ALVR105 (unless related to airway control)
15. Undergoing dialysis at any time during the screening period

Prior/Concurrent Clinical Study Experience

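### Under 12, a single viral-load draw at the Screening Visit conflicts with the 7-day rule for Cohort A/B allocation and with the weekly-testing text

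*Protocol*

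**What the plan says.** **Sampling under 12.** Footnote l of Table 1 (Protocol 1.3) states that children under 12 "years old will have only one blood draw during the Screening visit and will not have weekly blood draws". Footnote m limits the weekly screening-period samples to patients aged 12 and over. Pre-screening supplies nothing for this group: footnote a opens it only from age 12, and Section 2.3.2 adds that "Pediatric patients also do not participate in pre-screening blood samples".

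**Timing of the visit.** Footnote b of Table 1: "The Screening Visit could occur any time between the day of HCT and up to 42 (+7) days post-HCT". The column heading bounds it from the other side: "Up to 6 weeks before Study Drug Administration".

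**Cohort allocation.** In the synopsis, patients without detectable viremia go to Cohort A "based on the last viral load assessment available within 7 days prior to randomization". Cohort B, for viremic patients, has the same 7-day condition, and central laboratory results are to document status. Footnote j of Table 3, which is the schedule for children under 12, repeats that Cohorts A and B are randomized "based upon the last viral load assessed and within 7 days of randomization". Neither place makes an age exception.

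**Weekly testing.** The synopsis says "Patients will be tested once a week by the central laboratory during Screening until treatment assignment". Sections 4.1 and 8.1.2 say the same in substance, also with no age exception.

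**Exclusion 2.** Section 5.2 excludes patients with viremia for more than 3 viruses "from a central or local laboratory at any time during Screening prior to treatment assignment".

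**The concern.** Viremia status decides which randomized cohort a patient enters, so the age of the result is part of the cohort definition. From age 12, weekly sampling keeps the result current. Under 12 it is only as recent as the Screening Visit, and footnote b lets that visit follow the date on which participation is decided.

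A site that follows footnote l for a child screened two or more weeks ahead has two choices. It can leave the child unassigned, or it can assign on a result older than the protocol allows. In the second case a stale negative could place an already viremic child in Cohort A, the cohort meant to be free of detectable viremia. Section 2.2 cites viral reactivation in about 90% of allogeneic transplant recipients, so a change of status during screening is plausible.

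Exclusion 2 is also applied unevenly. It rests on one scheduled central sample under 12 and on weekly samples from age 12. The Cohort A/B split and the more-than-3-viruses exclusion could therefore mean somewhat different things in the two age groups.

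**Working it through.** The plan gives no figure to reproduce. The check is date arithmetic on its own windows.

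**Inputs**
- S, day of the only draw after transplant: 0 to 42 (+7) (Table 1, footnotes b and l).
- The visit is at most 42 days before the first dose (Table 1 column headings).
- A, day of treatment assignment: 15 to 42 (+7) (Section 5.1, criterion 5).
- Assignment is about 2 to 3 days before Day 1 (Table 3, footnote j).
- Condition for allocation: A − S ≤ 7 (synopsis; Table 3, footnote j).

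**Step 1: smallest possible age of the result.** For S ≤ 15 the minimum of A − S is 15 − S.
- S = 0: 15 days.
- S = 7: 8 days.
- S = 8: 7 days.

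A draw on any of days 0 to 7 therefore always fails. A draw on day 8 or later can comply, but only if assignment follows within 7 days.

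**Step 2: largest possible age.** The draw is at most 42 days before dosing, and assignment is 2 to 3 days before dosing: 42 − 2 = 40 and 42 − 3 = 39. The oldest result the schedule permits at assignment is about 40 days.

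**Step 3: share of children affected.** The documents give no distribution of intervals. As an assumption only, let the interval be uniform on whole days 0 to G. The share above 7 days is then (G − 7)/(G + 1).

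| G (days, assumed) | Share above 7 days |
|---|---|
| 7 | 0/8 = 0% |
| 14 | 7/15 = 47% |
| 21 | 14/22 = 64% |
| 28 | 21/29 = 72% |
| 40 | 33/41 = 80% |

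The spread shows that the share depends wholly on the assumption.

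**Step 4: can another scheduled sample supply the result?**
- *Repeat screening sample.* Footnote l wants repeat results in hand at assignment unless the Screening Visit was a week or less before treatment. Section 8.2.2 likewise accepts a single analysis only for patients screened within 7 days of assignment. No repeat is scheduled under 12.
- *Day 1 sample.* Footnote a of Table 3 lets Day 1 procedures be done in the 72 hours before dosing, but assignment is itself 2 to 3 days before Day 1. Central turnaround is not stated, so a result at assignment cannot be relied on.
- *Unscheduled sample.* Section 8 allows these for safety or technical reasons. Allocation is not among them. The same section rules out waivers.

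**Step 5: exclusion 2.** With a 40-day interval, strictly weekly sampling gives six samples from age 12 (days 0, 7, 14, 21, 28 and 35). Under 12 there is one.

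**The case against.** The best defence is that a compliant route exists. A site may hold the Screening Visit within 7 days of assignment, and a child screened then satisfies the 7-day rule with one draw, as Section 8.2.2 anticipates. If the timing is missed, Section 5.4 allows rescreening in consultation with the Medical Monitor. This stands, and it is why the affected share may be zero. It does not remove the conflict, because nothing directs sites to late screening and the weekly-testing text would still contradict footnote l.

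Further points limit the reach, and they stand:
- Text is blacked out in the inclusion criteria, Section 4.1, Section 8.2.2 and the randomization section. A rule for young children may sit there. The blacked-out text is not an error, but the visible passages would still disagree.
- Exclusion 2 counts local results too, and Section 8.1.2 and Appendix 2 accept local testing at screening. A child with more than 3 viruses may still be caught.
- Cohort OL takes either viremia status, and the SAP analyses only that cohort. No analysis in this SAP uses the A/B split.
- Reduced blood sampling in children is deliberate (Section 2.3.2) and is not in question here.

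A reader might infer three stronger things:
- *That many children cannot be assigned.* The documents give no counts or intervals to support this.
- *That a result could be 49 days old*, by pairing a day-0 visit with a day-49 assignment. The 6-week limit before dosing rules that out.
- *That a child who became viremic after screening would count as a prevention failure.* The primary endpoint is adjudicated clinically significant infection or end-organ disease. Viremia alone need not qualify, and Appendix 8 disregards JC viremia without clinical disease.

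**Conclusion.** The point holds as an internal contradiction in the protocol that affects allocation to randomized Cohorts A and B. Any child under 12 screened more than 7 days before randomization cannot meet the 7-day rule from scheduled samples. That includes every child drawn on days 0 to 7 after transplant. The result could be as much as about 40 days old. These statements rest only on the protocol's own windows.

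The number affected cannot be given. It is 0% if all intervals are 7 days or less, and the larger percentages above are illustrations. A stale negative could misplace a viremic child in Cohort A. The effect on exclusion 2 is fewer scheduled central samples under 12, partly offset by local results. The change should be made, because sites otherwise have instructions they cannot all follow.

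**What to change.** Reconcile Table 1 footnote l, Table 3 footnote j, the synopsis, Section 4.1 and Section 8.1.2 of the protocol:
- In footnote l, separate the under-12 draw from the Screening Visit as such. Time it so that the central result comes from within the 7 days before treatment assignment.
- Repeat the draw before assignment only if assignment slips beyond 7 days.
- In footnote j, refer to this draw as the source of the cohort-defining result under 12.
- Wherever weekly testing is described, state the under-12 exception.
- Check any blacked-out cohort criteria against the new wording.

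Leave SAP Table 5 unchanged. It reproduces the Amendment 2 schedule under which the Cohort OL data were collected, and editing it would misdescribe what was done.

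The cost is amendment wording. Children whose assignment keeps to the 7 days still have one draw. The downside is an occasional extra small-volume draw when assignment slips.
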